To our knowledge, this is the first study in which corticosteroids are administered immediately after the kidney biopsy in IgAN patients with active renal lesions. Based on the existing evidence from randomized clinical trials, the KDIGO guidelines suggest in those cases: RASBs for 3-6 months and then corticosteroids in presence of persistent proteinuria and $GFR >30$ ml/min/1.73 m². This therapeutic approach, although supported by evidence, may be a challenge based on empiric clinical knowledge supported also by findings of cohort studies. This demonstrates that after 3-6 months active renal lesions become chronic and consequently no association may be found between exposure to corticosteroids and clinical response for IgAN patients. In our randomized clinical study we compare the standard approach proposed by KDIGO guidelines (RASBs for 3-6 months followed by corticosteroids) vs a novel approach consisting of early corticosteroid therapy combined with RASBs from the beginning.

CHRONIgAN TRIAL

Patients with chronic (T1,2) or moderate renal lesions (M0,1; S0,1, E0, C0, T0) will be enrolled in a two-arm trial with 1:1 allocation ratio to compare Dapagliflozin combined with RASBs (experimental arm) versus corticosteroids combined with RASBs (control arm) after 4 run-in months of RASBs treatment. The enrolled patients will have proteinuria ≥ 0.5 g/day and GFR ≥ 30 ml/min/1.73 m².

Participants will receive study treatments by 4 weeks from the kidney biopsy.

Patients assigned to the experimental arm will receive RASBs therapy (4 run-in months) followed by Dapagliflozin (10 mg /day orally) combined with RASBs for a total of 32 consecutive months. Patients assigned to the control arm will receive RASBs therapy (4 run-in months) followed by oral corticosteroids therapy (prednisone) for six months (0.4 mg/kg body weight for 2 months and then gradual reduction of 5 mg/day for 4 months) and then RASBs alone for a total of 36 consecutive months.

This is a parallel group, two arm, superiority trial with 1:1 allocation ratio.

Rationale of the study design

We decided the combination Dapagliflozin and RASBs because recently, SGLT2is were administered in patients with type 2 diabetes and in other participants with CKD (some of them were affected by IgAN) (29-31). In these studies, the effect of SGLT2is was compared with a placebo.

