Patients will receive oral corticosteroids therapy for six months (prednisone 0.4 mg/kg body weight for 2 months and then gradual reduction of 5 mg/day for 4 months) combined with RASBs and, then, RASBs alone for a total of 36 consecutive months.

Rationale: To care the moderate and chronic renal lesions in non-responders to RASBs alone as suggested by the KDIGO guidelines (4,5).

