4.5 Participant timeline

Total Study duration: approximately 6 years:

- Enrollment period: 3 years
- Treatment and Follow-up period: 3 years + 30 days.

Figure 2A and **2B** illustrate the time schedule of enrollment, interventions, assessments and visits for participants.

Figure 2A. SPIRIT 2013 STATEMENT OF THE ACiGAN STUDY: Time schedule of the enrolment, interventions, assessments and visits of the participants.

Time point	STUDY PERIOD																			
	Enrolment	Allocation	Post-allocation														End of Treatment	End of Study		
			t ₁	t ₂	t ₄	t ₆	t ₈	t ₁₂	t ₁₅	t ₁₈	t ₂₁	t ₂₄	t ₂₇	t ₃₀	t ₃₃	t ₃₆				
	- t ₁	t ₀															t ₃₆	30 days after last treatment		
Enrolment:																				
Eligibility screen	x																			
Informed consent	x																			
Kidney biopsy	x																			
Laboratory data	x																			
Allocation		x																		
Interventions:																				
(A) Cs+RASBs (4 months) → RASBs			●	—————														●		
(B) RASBs (4 months) →Cs+RASBs (4 months)→RASBs			●	—————														●		
Assessments:																				
Serum creatinine	x		x	x	x	x	x	x	x	x	x	x	x	x	x	x	x			
eGFR	x		x	x	x	x	x	x	x	x	x	x	x	x	x	x	x			
Daily proteinuria	x		x	x	x	x	x	x	x	x	x	x	x	x	x	x	x			
Adverse events	x		x	x	x	x	x	x	x	x	x	x	x	x	x	x	x		x	
Concomitant medications	x		x	x	x	x	x	x	x	x	x	x	x	x	x	x	x		x	
Outcome variables:																				
Proteinuria reduction (primary end point)						x	x	x	x	x	x	x	x	x	x	x	x	x		
eGFR slope reduction (secondary end point)			x	x	x	x	x	x	x	x	x	x	x	x	x	x	x	x		
Biological samples collection		x	x	x	x	x	x	x				x				x				

Figure 2B. SPIRIT 2013 STATEMENT OF THE CHRONIGAN STUDY: Time Schedule of the enrolment interventions, assessments and visits of the participants.

Time point	STUDY PERIOD															
	Enrolment	Allocation	Post-allocation												End of Treatment	End of Study
	- t ₁	t ₀	t ₁	t ₄	t ₈	t ₁₀	t ₁₂	t ₁₄	t ₁₈	t ₂₄	t ₂₇	t ₃₀	t ₃₃	t ₃₆	t ₃₆	30 days after last treatment
Enrolment:																
Eligibility screen	x															
Informed consent	x															
Kidney biopsy	x															
Laboratory data	x															
Allocation		x														
Interventions:																
(A) RASBs (4 months)→ Dapagliflozin +RASBs			●	—————											●	
(B) RASBs (4 months)→ Cs+RASBs(6 months)→RASBs			●	—————											●	
Assessments:																
Serum creatinine	x		x	x	x	x	x	x	x	x	x	x	x	x		
eGFR	x		x	x	x	x	x	x	x	x	x	x	x	x		
Daily proteinuria	x		x	x	x	x	x	x	x	x	x	x	x	x		

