6.1 Recruitment

Rationale: In some RCTs (22,23) IgAN patients received three - six months of RASBs treatment before their enrollment for corticosteroid therapy. In our opinion this approach is not correct because the active renal lesions evolve in the chronic stage and are no-responsive to corticosteroid therapy. Therefore, the aim of our RCT is early treatment of the active renal lesions because they are responsible for altered GFR and proteinuria.

Recruitment: IgAN patients will be enrolled within 2-4 weeks from the kidney biopsy in renal centers. The kidney biopsy will be scored according to the Oxford classification (6-8) because it is a simple method for predicting renal outcomes and for scoring active and chronic renal lesions (46). Therefore, the kidney biopsy will be the principal key-note, not only for diagnosis but also for personalized therapy, because active renal lesions (E1,C1) will be treated with immediate corticosteroid therapy before lesions become chronic.

The kidney biopsy will be analyzed using digital histopathologic analysis coupled with machine-learning tools. At least eight glomeruli will be available for a correct diagnosis. Immunofluorescence technique will be used to determine the relevance of mesangial IgA deposits in the glomeruli. Renal tissue sections will be stained with hematoxylin and eosin, periodic acid-Schiff and methenamine silver. The last edition of the Oxford classification (MESTC) (8) will be used for the scoring of the renal lesions. Active renal lesions are endocapillary (E) and extracapillary (C) proliferative lesions while T lesions (T1,2) are expression of chronic renal lesions and severe outcome (46-49). Other histological lesions will be evaluated as fibrinoid necrosis, global glomerulosclerosis and arteriolosclerosis.

Three independent renal pathologists, blinded to the study results, will score the lesions in the kidney biopsy using the Aperio System. The histology report will be necessary for the enrollment of patients. No larger RCT has confirmed that the disease improves when clinical decisions are made in a short time in the presence of the MESTC score.

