6.2 Allocation

After initial eligibility based on screening of the clinical data and kidney biopsy report, each patient will receive an explanation of the trial plan. After the signature of the consensus participation the patient will be enrolled and randomized separately in each trial (allocation 1 to 1 ratio) via a web-based program generating random numbers to ensure allocation concealment. Stratified randomization will be done by age and sex in renal centers. The follow-up study to measure the outcomes will consist of regular visits at the prescribed times to collect clinical and laboratory data and information on drug adherence. Before the trial is complete, each patient will receive a final outpatient visit.

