6.3 Blinding

Allocation concealment will not be blinded to the group of the assignment.

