6.5 Analysis populations

The primary trial efficacy analysis will be done in the intention-to-treat (ITT) population, including all randomly assigned participants.

A secondary analysis will be performed in the persistent population (PP, i.e. including all patients who persisted on the investigational drugs for at least 4 and 8 months (ACiGaN trial) or 10 months (CHRONiGaN trial).

Patients who need to change their study treatment prior to 1st month (ACiGaN trial) or 4 months (CHRONiGaN trial) will be considered as dropouts.

The safety population will be represented by all patients receiving at least one dose of the investigational drugs.

A recent systematic review (15) evidenced that patients with histological lesion M1 were responsive to corticosteroids. Therefore, we will do a subgroup analysis to evaluate the effect of corticosteroids in active and chronic IgAN patients with lesion M1 versus M0.

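### CHRONiGaN allocates patients open-label before a 4-month RASB run-in that is the same in both arms, so run-in losses and allocation-aware behaviour fall inside the randomised comparison

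*Protocol*

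**What the plan says.** **When patients are allocated.** Section 6.1: "IgAN patients will be enrolled within 2-4 weeks from the kidney biopsy in renal centers". Section 6.2: "After the signature of the consensus participation the patient will be enrolled and randomized separately in each trial". Figure 2B (Section 4.5) has its allocation column at t0 and lists t1 and t4 as post-allocation. Section 6.3 confirms that assignment is known: "Allocation concealment will not be blinded to the group of the assignment".

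**What happens in months 0 to 4.** Section 3: "Patients assigned to the experimental arm will receive RASBs therapy (4 run-in months) followed by Dapagliflozin". The control arm receives the same RASB period before prednisone, and its line in Figure 2B reads "B) RASBs (4 months)→ Cs+RASBs(6 months)→RASBs".

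**The outcome.** The primary endpoint is the between-arm difference in 24-hour proteinuria reduction, at 10 months in Section 4.4 and at 12 months in Section 6.4. Section 6.4 measures it from a baseline that it does not define. Figure 2B schedules proteinuria at -t1, leaves t0 blank, and schedules it again at t1, t4, t8, t10 and later.

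**Who is analysed.** Section 6.5 includes all randomised patients in the primary analysis. It also says that patients whose treatment must change before "or 4 months (CHRONiGaN trial) will be considered as dropouts".

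**Who receives steroids.** Section 4.3.1 gives the rationale for CHRONiGaN corticosteroids as "To care the moderate and chronic renal lesions in non-responders to RASBs alone as suggested by the KDIGO guidelines". Section 3 gives them to every control patient, with no month-4 check.

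**The concern.** A run-in normally precedes randomisation, so that patients who drop out or prove unsuitable never enter the comparison. Here it follows. Three consequences are possible.

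- **Dilution.** A patient who leaves before month 4 has received neither dapagliflozin nor corticosteroids, but is analysed as randomised. Such patients pull the estimated difference towards zero.
- **Behaviour that depends on allocation.** For 4 months, patients and sites know whether steroids or dapagliflozin will follow, while RASBs are being titrated to effect. Titration intensity or withdrawal could differ between arms before the treatments diverge.
- **Noise.** If the change is measured from enrolment, it includes the RASB response, which says nothing about the compared drugs. The time-averaged proteinuria endpoint also includes run-in values, because it uses all post-randomisation measurements.

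CHRONiGaN's sample is described as opportunistic and has no effect size, SD or power, so the plan states no margin to absorb these losses.

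**Working it through.** **1. The plan's own figures.** CHRONiGaN's 300 (150 per arm, including 10% dropout) has no inputs and cannot be reproduced. The ACiGaN figure in Section 6 can: n = 2(1.960 + 1.282)² × (1.0/0.6)² = 58.4, rounded up to 59 per arm. Then 59/0.9 = 65.6, rounded up to 66 per arm, or 132 in total, as stated. The same dropout convention gives CHRONiGaN 150 × 0.9 = 135 evaluable per arm.

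**2. Order of events.** Consent and randomisation come within 2-4 weeks of biopsy, followed by 4 identical RASB months and then 6 months on the compared drugs. Since 4 + 6 = 10, the month-10 endpoint is counted from before the run-in. The share of the window spent on identical treatment is 4/10 = 40%, or 4/12 = 33% with the Section 6.4 time point.

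**3. Reference case.** The detectable difference in SD units is (z for α + z for power) × √(2/135), two-sided 5%.
- 80% power: 2.802 × 0.1217 = 0.341 SD
- 90% power: 3.242 × 0.1217 = 0.395 SD

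**4. Dilution by run-in loss.** Let q be the share of analysed patients who never start the compared drug and contribute no effect. The effect becomes (1 - q) times its size, and power = Φ(3.242(1 - q) - 1.960). The number per arm that restores 90% is 135/(1 - q)², divided by 0.9. The protocol gives no loss rate, so q is assumed.

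| q | Power | Randomised per arm to restore 90% |
|---|---|---|
| 0 | 90% | 150 |
| 5% | 87% | 167 |
| 10% | 83% | 186 |
| 15% | 79% | 208 |
| 20% | 74% | 235 |

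**5. Precision.** Let r0 and r4 be the correlations of month-10 proteinuria with the enrolment and month-4 values. Assume equal variances (scaled to 1), r0 of 0.4-0.5 and r4 of 0.6-0.7. None of these is in the protocol.
- Change from enrolment: 2(1 - r0) = 1.20 or 1.00
- ANCOVA on enrolment: 1 - r0² = 0.84 or 0.75
- Change from month 4: 2(1 - r4) = 0.80 or 0.60
- ANCOVA on month 4: 1 - r4² = 0.64 or 0.51

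| r0, r4 | Cut: change from month 4 vs change from enrolment | Cut: ANCOVA on month 4 vs change from enrolment | Cut: ANCOVA on month 4 vs ANCOVA on enrolment |
|---|---|---|---|
| 0.4, 0.6 | 33% | 47% | 24% |
| 0.4, 0.7 | 50% | 58% | 39% |
| 0.5, 0.6 | 20% | 36% | 15% |
| 0.5, 0.7 | 40% | 49% | 32% |

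Take SD 1.0 g for the change from enrolment. This is borrowed from ACiGaN at 6 months, since CHRONiGaN has none. The difference detectable with 80% power is then 0.34 g now. With the change from month 4 it is 0.341 × √0.50 = 0.24 g to 0.341 × √0.80 = 0.31 g. With ANCOVA on month 4 it is 0.341 × √0.425 = 0.22 g to 0.341 × √0.64 = 0.27 g.

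**6. Sensitivity of step 5.** If r0 = r4, moving the baseline gains nothing. Equivalently, let the run-in change have SD s relative to the on-treatment change, and let c be their correlation. The SD of the total change is √(1 + s² + 2cs). With c = 0 and s from 0.25 to 1.0, a 90% power falls to between 88% and 63%. With c = -0.5 it stays at 90-96%. The sign of the noise effect is therefore not fixed by the protocol.

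**The case against.** **Allocation may follow the run-in.** Sections 1.2 and 3 speak of a comparison after 4 run-in months, which alone could mean later randomisation. Section 6.2, the description of already-assigned patients in Section 3, and Figure 2B all point to t0. That reading therefore fails, but the wording should be made unambiguous.

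**The design compares whole strategies from biopsy.** That is legitimate in general. It carries little weight here because the first 4 months are the same in both arms by design.

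**The 10% allowance already covers run-in losses.** Section 6.5 calls them dropouts, so it may. The protocol does not divide the allowance between the run-in and the 6 treatment months, and no run-in loss rate is given. This limits the dilution result to a range under assumptions.

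**A reader might infer that the comparison is biased.** The protocol does not support that. All patients analysed were randomised, and intention-to-treat from allocation remains valid. Differential titration or withdrawal is an opportunity that the design leaves open, not a demonstrated effect.

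**A reader might infer that the protocol takes the change from t0, and that this necessarily adds variance.** Neither follows. Baseline is undefined and no proteinuria is scheduled at t0; a start at -t1 is an inference, though the natural one. Step 6 shows that the variance effect can be nil or reversed. Part of the ANCOVA gain also needs no design change: adjusting for the enrolment value alone cuts variance by 25-30% under the same assumptions (1.00 to 0.75, or 1.20 to 0.84).

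**Conclusion.** The concern holds as a design weakness, not as a fault that invalidates the trial. Open-label allocation before 4 months of identical treatment is documented. The loss effect runs in one direction: if 5-20% of those analysed never start the compared drug, 90% power for 0.39 SD falls to about 87-74%. This assumes 135 evaluable per arm, no effect in those patients, and a loss rate the protocol does not give.

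The precision gain is conditional on the correlations, equal variances and borrowed SD in step 5. Under these, the variance of the change falls 20-50%. With ANCOVA on month 4 it falls 36-58% against the unadjusted change, but only 15-39% against ANCOVA on enrolment. Under other correlations the gain can vanish, so it supports the change but is not the main reason for it.

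Separately, Sections 3 and 4.3.1 contradict each other on whether CHRONiGaN corticosteroids are for all control patients or only for those who do not respond to RASBs.

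**What to change.** 1. Move CHRONiGaN allocation to the end of the RASB run-in (month 4). Define the month-4 24-hour proteinuria, already scheduled in Figure 2B, as baseline. Analyse proteinuria after the 6 treatment months by ANCOVA on that value.
2. For patients already randomised before the run-in, or if allocation cannot move, adjust the primary analysis only for the pre-randomisation (-t1) proteinuria. Month-4 proteinuria is then an open-label post-randomisation value that assignment may have influenced, and it is missing for patients lost earlier. Use adjustment for it only as a sensitivity analysis.
3. In either case, define baseline explicitly, settle the 10- versus 12-month time point, and reconcile Section 3 with Section 4.3.1 on who receives corticosteroids. The clinical rule is for the sponsor to settle.

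**Cost.** A protocol amendment, a changed trigger in the web randomisation, and slightly more screening, because some patients will leave before allocation. The randomised population becomes run-in completers, which narrows the question. Visit times, time-averaged proteinuria and the 36-month follow-up clock must be re-anchored to the new allocation date. The fallback in item 2 needs no new data.

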4. PARTICIPANTS, INTERVENTIONS AND OUTCOMES

4.1 Study setting

Patients aged 18 to 75 years, with biopsy-proven IgAN will be eligible to participate in the study.

4.2 Eligibility criteria

Inclusion and exclusion criteria are listed below. Patients will be enrolled in a time frame of three years and the duration of the follow-up will be three years.

4.2.1 Inclusion criteria

4.2.1.1 ACIgAN study

1. Males and females aged 18 to 75 years.
2. Written informed consent form.
3. Biopsy-proven idiopathic IgAN with active renal lesions (E1 and/or C1) within 2 weeks.
4. eGFR ≥ 30 ml/min/1.73 m².
5. 24-hour proteinuria ≥ 0.5 g.
6. Patients on treatment or candidate for the treatment with RASBs (either an ACEi or ARB), as per clinical practice, according to the current KDIGO guidelines

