Referenced studies (10-15) seem to fit some of the Bradford Hill criteria (21) for the ascertainment of causality, specifically i) there are several observational retrospective studies (10-12) and a prospective study (14) and a systematic review (15) exploring the association between the type of kidney biopsy lesions and response to immunosuppressive treatment; ii) there is consistency across studies in the findings that active lesions may respond to immunosuppression as opposed to chronic lesions, data which have been identified by researchers from different countries in the world; iii) there is a strong association between different type of renal lesions and response to immunosuppressive therapy. In view of well established pragmatic clinical experience and the number, consistency and strength of the findings of observational studies, there seems to be scientific equipoise for the design and conduct of a randomized trial of interventions for IgA nephropathy based on the findings of kidney biopsy.

What is not known

There are no randomized data on the different treatment of active and chronic renal lesions in IgAN patients. The last RCTs using steroids (STOP IgAN and TESTING) (22,23) did not evaluate the type of lesions in the kidney biopsy at the enrollment time. Patients with active and chronic renal lesions all received the same treatment approach, independent of kidney biopsy findings. In consideration of this, recently, the researchers of the TESTING study have programmed a post-hoc analysis to evaluate the effect of therapy on renal lesions (24).

In STOP IgAN and TESTING studies, patients were enrolled after 3-6 months of RASB therapy, as per the current standard care. A recent histology study (25) based on two consecutive protocol kidney biopsies showed the dynamic changes of active and chronic renal lesions during the clinical course of the disease. Therefore, after 3-6 months active renal lesions not only in IgAN but in other glomerulonephritis (ie lupus nephritis) become chronic and corticosteroids may therefore not exert any role. This point has been commented by Troyanov et al (26) in a recent paper published by Itami et al (13) although needs to be formally explored in the setting of an experimental randomized trial.

Why this study

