6. SAMPLE SIZE AND STATISTICAL METHODS

ACIGAN. Data from the literature (22,23) have shown a difference in renal survival between corticosteroids and controls when the researchers assumed a difference of 50% in the primary end point (i.e. in the between-arms difference of delta 24 hour proteinuria from baseline to 6 months) as clinically relevant. Therefore, we assume that a mean delta proteinuria from baseline to 6 months in patients treated with RASBs alone (control arm) is 0.6 ± 1.0 g/24 hours (\pm SD) versus a mean delta proteinuria that is 1.2 ± 1.0 g/24 hours (\pm SD) from baseline to 6 months in patients treated with RASBs and corticosteroids (experimental arm). Based on these assumptions, we calculated a sample size of

132 patients (66 patients per group including a 10% dropout rate) for a power of 90%, a two-sided significance level of 0.05 and 3 years of recruitment. If the number of the enrolled patients will be insufficient, the recruitment period will be extended for two years.

CHRONiGaN. Data from the literature (29-31) have shown a difference of renal survival between SGLT2is and controls. There are no data in the literature exploring the difference of renal survival or proteinuria between SGLT2is and steroids. Here, the researchers assumed an opportunistic sample of 300 patients for this first comparative study (150 patients per group, including a 10% dropout rate).

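### ACiGaN enrols both patients already on RASBs and patients starting them, yet its primary comparison of change in proteinuria is unadjusted for RASB status at entry, which costs precision

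*Protocol*

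**What the plan says.** - **Entry.** Section 4.2.1.1, criterion 6, admits "Patients on treatment or candidate for the treatment with RASBs (either an ACEi or ARB), as per clinical practice". It states no minimum prior exposure, stable dose or washout.
- **Design.** Section 3 starts steroids in the experimental arm within two weeks of biopsy, while the control arm has RASBs alone for four months. ACiGaN has no RASB run-in; CHRONiGaN gives both arms four months of RASBs before the compared drugs begin. In ACiGaN, RASBs are to be titrated in every patient for their effect on proteinuria.
- **Planning values.** Section 6 assumes that the mean fall in "patients treated with RASBs alone (control arm) is 0.6" g/24 h, "versus a mean delta proteinuria that is 1.2" g/24 h with steroids added, each with an SD of 1.0. It does not say whether these values describe patients starting RASBs, patients already on them, or a mixture.
- **Randomisation.** Section 6.2: "Stratified randomization will be done by age and sex in renal centers".
- **Analysis.** Section 6.4 compares continuous variables between arms by independent t-test or Mann-Whitney test and reports the primary endpoint as a mean difference with 95% CI. No covariates are named for the secondary mixed or GEE models. The covariate list given there belongs to the Cox model and does not include RASB status at entry.
- **Data.** Figure 2A schedules concomitant medications at enrolment.

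**The concern.** The primary outcome is change from a baseline taken at entry. For a patient who starts RASBs then, the whole response to the RASB falls after baseline. For a patient already on them, part of that response is already in the baseline value. The protocol's own planning makes this response substantial: 0.6 g/24 h for RASBs alone, as large as the 0.6 g/24 h by which steroids are expected to add to it. A baseline factor that shifts the outcome by an appreciable amount, and that the comparison ignores, stays in the error variance and can by chance differ between arms in a trial of 132. At stake is some power and some clarity of interpretation, both of which can be recovered from data already being collected.

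**Working it through.** **Inputs from the protocol (Section 6).** Difference 1.2 − 0.6 = 0.6 g/24 h; SD 1.0; two-sided alpha 0.05; power 90%; 10% dropout; 66 per arm.

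**Step 1: reproduce the plan.** n per arm = 2 × (1.960 + 1.282)² × 1.0² / 0.6² = 58.4, so 59. Allowing for dropout, 59 / 0.9 = 65.6, so 66 per arm and 132 in total. This matches. Power with 59 evaluable per arm is 89.8% by the noncentral t distribution (90.3% by the normal approximation). The arithmetic of the plan is sound.

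**Step 2: variance carried by RASB status.** Let q be the share already on RASBs and g the gap in mean fall between patients starting RASBs and patients already on them. The between-group variance is q(1 − q)g². The protocol gives neither q nor g, so both are assumptions: q = 0.5, and g = 0.3, 0.6 or 1.0 g/24 h. The middle value equals the planned control fall; the lowest allows for RASB titration also lowering proteinuria in patients already treated. The steroid effect is held at 0.6 in both groups.

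- g = 0.3: 0.25 × 0.09 = 0.0225
- g = 0.6: 0.25 × 0.36 = 0.09
- g = 1.0: 0.25 × 1.00 = 0.25

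**Step 3: power with 59 per arm (noncentral t).** There are two readings of the planned SD.

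*Reading 1: SD 1.0 already covers the mixed population.* Unadjusted power stays at 89.8%. The adjusted residual SD is √(1 − q(1 − q)g²).

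*Reading 2: SD 1.0 holds within each RASB group.* Adjusted power is about 89.8%. The unadjusted SD is √(1 + q(1 − q)g²).

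| g (g/24 h) | Reading 1: adjusted SD | Reading 1: adjusted power | Reading 2: unadjusted SD | Reading 2: unadjusted power |
|---|---|---|---|---|
| 0.3 | 0.989 | 90.5% | 1.011 | 89.2% |
| 0.6 | 0.954 | 92.3% | 1.044 | 87.2% |
| 1.0 | 0.866 | 96.2% | 1.118 | 82.4% |

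Adjustment is at least as good under both readings. The degree of freedom it uses is negligible at this size.

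**Step 4: chance imbalance.** With q = 0.5, the difference between arms in the share already on RASBs has a 95% range of ±1.96 × √(2 × 0.25 / 59) = ±0.18. Multiplied by g, this shifts the unadjusted difference by up to about ±0.05, ±0.11 or ±0.18 g/24 h, against a planned effect of 0.6. This is the same cost as in Step 3 seen in a single realised trial; it is not an additional one.

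**The case against.** Several objections have force.

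- **The power formula needs only the mean difference and the SD.** Both may describe a mixture, and the level of the control fall does not enter. If SD 1.0 is the mixed SD, the plan has the power it claims and adjustment is a bonus. This stands.
- **Randomisation balances RASB status in expectation.** This stands; no systematic bias is claimed.
- **Patients already on RASBs may also improve.** Titration applies to every patient, so g may be small. This stands too. At 0.3 g the cost is under one percentage point. A reader might infer that such patients receive no further RASB effect, but Section 3 does not support that.
- **Covariates are often left to an analysis plan.** True, and one that is not at hand may add them. But Section 6.4 does name the test, and that test is unadjusted.

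Three stronger readings are tempting and should be resisted. First, a reader might infer that the 0.6 g control fall was taken from the cited steroid trials, in which "patients were enrolled after 3-6 months of RASB therapy, as per the current standard care". Section 6 cites those trials for the relevance of a 50% difference and then states its own assumption, so a mismatch of populations is not established. Second, a reader might suppose a proportional steroid effect and infer a much larger loss of power. The documents give no percentage reduction for RASBs. The direction also depends on the model: power falls with a larger naive share if steroids remove a fraction of remaining proteinuria, and with a larger pretreated share if they double the control fall. Third, a reader might conclude that RASB status should replace age as a stratum. That is a preference; with over 30 sites and 132 patients, about four per site, another within-centre stratum might balance little.

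**Conclusion.** The point holds as one of precision and chance imbalance. ACiGaN mixes two groups that plausibly differ in the primary outcome, and the stated primary comparison ignores the difference. With half naive and a constant 0.6 g effect, for gaps of 0.3 to 1.0 g, adjustment gains between under 1 and about 6 percentage points of power if SD 1.0 covers the mix, or avoids a loss of under 1 to about 7 points if it does not. These sizes rest on an assumed mix and an assumed gap, neither of which the protocol gives. The sample size of 132 reproduces and the 90% power is not shown to be wrong. What the protocol leaves unclear is which population its planning values describe.

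**What to change.** 1. Code RASB status at entry (naive or already treated) from the concomitant medications recorded at enrolment.
2. In Section 6.4, replace the unadjusted test for the ACiGaN primary endpoint with a linear model of change in 24-hour proteinuria on treatment arm, baseline proteinuria and RASB status at entry, reporting the adjusted mean difference with its 95% CI.
3. In Section 6, state whether the 0.6 g control fall and the SD of 1.0 refer to the mixed population, and if so what mix is assumed.

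The cost is one derived variable, two covariates and a sentence. No treatment, visit, stratification factor or sample size has to change. The definition of RASB status should be fixed before outcome data are examined.
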